4 TRIAL POPULATION

The study population will be up to 19 patients above the age of 18 with moderate to severe AKC, VKC or severe allergic conjunctivitis (SAC or PAC). Patients may be male or female.

4.1 Inclusion Criteria

- 1. Aged 18 and above
- 2. Diagnosis of moderate to severe AKC,VKC or severe allergic conjunctivitis (seasonal or perennial). Defined as:
 - AKC, VKC a composite symptom/sign score from one eye of ≥ 18 out of 33 (see Clinical Scoring 17.1)
 - Severe allergic conjunctivitis a composite symptom/sign score from one eye of \geq 15 out of 27 (see Clinical Scoring Section 17.1)
- 3. Will have had received some topical therapy during the last 3 months without improvement but will not currently be receiving systemic immunotherapy. Topical therapy may be topical calcineurin inhibitors, antihistamines or corticosteroids alone or in combination. Lubricants or artificial tears will not a count as topical therapy for these purposes.
- 4. Will have had at least 7 days without topical ocular corticosteroids prior to entry
- 5. Willing to give informed consent
- 6. Willing to use highly effective contraceptive precautions for the duration of the study and for 90 days after the last dose of IMP.
- 7. Willing to avoid prohibited medications for duration of study (see list of prohibited medications)

4.2 Exclusion Criteria

- 1. Eye surface disease other than AKC, VKC or severe allergic conjunctivitis (SAC or PAC)
- 2. Contact lens use during the study
- 3. Complete or partial tarsorrhaphy. If such a procedure becomes necessary during the course of the trial patients may remain in the trial providing that at least 50% of the eye surface remains visible to slit lamp examination
- 4. Ankyloblepharon of any degree at entry to the trial
- 5. Known or suspected ocular malignancy
- 6. Active ocular infection at entry to the trial. Patients with eye surface bacterial, viral, fungal or protozoal infection may enter the trial after elimination of the infection as confirmed by eye swabs
- 7. Known or suspected uveitis
- 8. Participation in any other clinical trial within 1 month of enrolment
- 9. Use of any of the following prohibited medications:
 - Eculizumab
 - Any other investigational complement inhibitor whether systemic or topical (e.g. RA101495)
 - Montelukast
 - Zafirlukast
 - Pranlukast

– Zileuton

- Hypericum perforatum (St John's wort)
- 10. Corneal perforation
- 11. Uncontrolled glaucoma (increase in dose of glaucoma medication or surgical intervention for glaucoma within 3 months prior to entry)
- 12. Pregnancy (females)
- 13. Breast feeding (females)
- 14. Known allergy to ticks or severe reaction to arthropod venom (e.g. bee or wasp venom)
- 15. Use of topical optical steroids within 7 days of the Screening Visit
- 16. Failure to satisfy the PI of suitability to participate for any other reason

4.3 Concomitant Therapy

At screening, the PI will ask the patient about any current ongoing medications. During the course of the study, patients should be reminded to record any concomitant medications in their patient diaries and the PI should discuss medications at each visit. All concomitant medications, including herbal and vitamin supplements, must be recorded into the electronic case report form (eCRF).

All patients may use an eye lubricant *pro re nata* (p.r.n.). This should not be given within 15 minutes before or after rVA576. The exact choice of lubricant is left to the patient but the following are recommended:

Unpreserved carmellose 1% (e.g. Cellusan) Unpreserved sodium hyaluronate ~0.1% (e.g. Hylo-Tear) Unpreserved sodium hyaluronate ~0.2% (e.g. Hylo-Forte)

4.3.1 Prohibited Medications

Use of systemic immunosuppressives, antihistamines or corticosteroids during the trial is forbidden. Other drugs acting directly on the complement or eicosanoid systems either topically or systemically including;

- Eculizumab
- Any other investigational complement inhibitor whether systemic or topical (e.g. RA101495)
- Montelukast
- Zafirlukast
- Pranlukast
- Zileuton
- Hypericum perforatum (St John's wort)

4.3.2 Neisseria immunisation and antibiotic prophylaxis

Neisseria meningitidis immunisation and antibiotic prophylaxis are not considered necessary for patients participating in this trial because the maximum dose of rVA576 that patients would be exposed, to even if the total dose from both eyes was to be systemically absorbed, would be 0.1mg. The dose needed to completely ablate the terminal complement system in a 70kg adult is approximately 40mg and it is considered that 0.1mg would have no inhibitory effect on systemic innate immunity.

4.4 Contraception

There are no specific, identified risks to mother or foetus from rVA576 therapy. A segment 1 reproductive toxicology study has been undertaken in mice (YUU0001) to assess the effects of 0, 0.5, 5 and 10 mg/kg/day rVA576 on the fertility and early embryonic development of the mouse when administered for at least 14 days before and during pairing, and then to Day 6 of gestation in females and until the day before necropsy for males. The study reported no deaths or clinical signs considered to be associated with the doses of rVA576 test; the causes of death for 1 male and 1 female found dead during the study were considered to be unrelated to test item administration. There was no effect of rVA576 on body weight, food intake, mating activity, fertility and mating, pregnancy or uterine implantation. There were no findings at necropsy considered to be related to rVA576 and group mean ovary and testes weights for animals given the test item were similar to Controls. Segment 2 and 3 reproductive toxicology studies are completed, patients being treated with rVA576 should be advised to use the following precautions against sexual exposure and pregnancy.

All trial participants (male and female) of childbearing potential must use, with their partner, a combination of an approved method of highly effective contraception with at least one barrier method of contraception from the time of signing the Informed Consent Form (ICF) until 90 days after the last dose of rVA576. Women of child bearing potential are considered those women who have menarche and until becoming post-menopausal unless permanently sterilised. Permanent sterilisation methods include hysterectomy, bilateral salpingectomy, and bilateral oophorectomy. A postmenopausal state is defined as no menses for 12 months without an alternative cause.

The following methods of highly effective contraception are acceptable and must be combined with at least one of the barrier method of contraception:

- Surgical sterilisation (i.e. bilateral tubal removal, bilateral ovary removal, hysterectomy for female partners; vasectomy for males)
- Placement of an intrauterine device or intrauterine system
- Hormonal contraception associated with the inhibition of ovulation (implantable, patch, oral)
- Barrier methods:
 - For male patients, this must be a condom; for female patients, either their partner's use of a condom or the patient's use of an occlusive cap [diaphragm or cervical/vault caps] with spermicidal foam/gel/film/cream/suppository
 - Barrier methods must be used in conjunction with a highly effective method of contraception listed above

Alternatively, true abstinence is acceptable when consistent with the patient's preferred and usual lifestyle. Any female patient who becomes pregnant during the course of the trial will be withdrawn from the trial.

Male patients who have been sterilised are required to use one barrier method of contraception (condom).

4.4.1 Exposure of Partners During the Study

There is a risk of drug exposure through ejaculate (which also applies to vasectomised males) which might be harmful to the sexual partners, including pregnant partners of male patients. A

combination of an approved method of highly effective contraception with at least one barrier method of contraception should be used throughout the study and for 90 days after the last day of IMP administration.

4.4.2 Sperm Donation

Male patients should not donate sperm for the duration of the study and for at least 90 days after the last day of IMP administration.

4.4.3 Egg Donation

Female patients should not donate eggs for the duration of the study and for at least 90 days after the last dose of IMP administration.

4.4.4 Breast Feeding

Female patients should not breast feed infants for the duration of the study and for at least 90 days after the last day of IMP administration.

5 TRIAL OBJECTIVES AND ENDPOINTS

5.1 Trial objectives

Part 1: An additional objective for the first 3 patients is to allow the P.I. to assess the patients' ability to use the eye dropper and vials correctly

Part 1 and Part 2: The primary trial objective is to demonstrate the safety and tolerability of rVA576 when given by topical ocular administration to patients with AKC, VKC, and severe allergic conjunctivitis (SAC or PAC).

The secondary objective is to demonstrate efficacy in this patient population in Part 2 of the study.

To assess whether rVA576 0.25% eye drops, solution is effective in mitigating the signs and symptoms of AKC, VKC, and severe allergic conjunctivitis (SAC or PAC) and whether they have any effect on surrogate markers of inflammation.

Efficacy will be defined as a difference in the mean composite clinical score between active and placebo treated patients in part 2 of the study. Clinical assessments and safety assessments in the randomised part of the study will be performed by a masked reviewer

5.2 Endpoints

5.2.1 Primary endpoint

• Incidence of ocular treatment emergent adverse events during the treatment period (adverse events which have occurred during the 56 days following randomisation (Part 2 of the study only) will be considered in the analysis of the primary safety outcome).

5.2.2 Secondary endpoint

- Post-instillation comfort, as graded on patient diary cards at the following intervals Days 1-14, Day 15-28, Day 29-42 and Day 43-56
- Visual acuity by Early Treatment Diabetic Retinopathy Study (ETDRS) charts comparison from Day 1 to Day 56
- Change from Day 1 in composite clinical scores at Day 14, 28, 42 and 56
- Number and percentage of patients with MMP-9 positive levels at Days 1, 28, and 56
- Change from Day 1 in Tear film break up time (TBUT) at Day 14, 28, 42 and 56

5.2.3 Exploratory endpoints

- Systemic absorption by blood sampling
- If enough tear fluid can be collected analysis of complement C3, C5 and LTB4 will be performed
- A comparison of the number of patients requiring rescue therapy at any stage of the trial and the number on such therapy at the end of the trial
- Comparison of the Conjunctival impression cytology results in each treatment group from Day 1 to Day 56 using flow cytometry analysis [NB Because these may not be reported for some time after completion of the trial and database lock, they will not form part of the statistical analysis and will be used for research information only]

6 TRIAL DESIGN AND PROCEDURES

6.1 Trial Design

The trial will comprise 2 parts:

Part 1: The first 3 patients selected for the study will be treated with active drug in open-label manner. They will have weekly clinic visits for up the first 2 weeks and thereafter biweekly visits. When the third of the first 3 patients has completed their first 2 weeks treatment, the PI will review the safety, tolerability and ease of application for each patient before deciding to proceed to the randomised, double masked comparative phase of the study (Part 2). The 3 patients will continue on the study and complete the 8 weeks trial as open label patients.

Part 2: A randomised, double-masked, placebo controlled trial of topical rVA576 or placebo eye drops in moderate to severe AKC, VKC and severe allergic conjunctivitis (SAC or PAC). The part 2 trial population will comprise 16 patients who meet all the inclusion and none of the exclusion criteria (Section 4.1 and Section 4.2).

6.2 **Duration of trial**

The estimated duration of the study for an individual patient is approximately 13 weeks. The duration from the First Patient Screened to Last Patient Last Visit (LPLV) will be approximately 7-8 months.

At the end of the 56 Days the subjects will return to their usual standard of care therapy, as this is the first clinical trial of rVA576 in patients with AKC, VKC and severe allergic conjunctivitis (SAC or PAC) and the long-term efficacy and safety is not yet established.

Figure 6 Trial Design

TRACKER Trial Design

Protocol AK701 - version 8.0 10 February 2020 © Akari Therapeutics Plc

6.3 Dosing Scheme

Part 1: The product will be supplied as a sterile 0.25% solution in 6 mL glass vials containing 1 mL of rVA576 solution. Single use eye dropper pipettes will also be supplied. The vials are for single use (one drop to each eye) and must be retained and returned to the site at each clinic visit.

Part 2: The product will be supplied as a sterile 0.25% solution in 6 mL glass vials containing 1 mL of solution of either rVA576 or placebo. Eye dropper pipettes will also be supplied. The vials are for single use (one drop to each eye) and must be retained and returned to the site at each clinical visit.

The patients will be randomised to receive either rVA576 active or placebo in double masked fashion. The product should be administered as one drop to each eye every 12 hours (i.e. twice daily) for a total of 56 days.

The product should be stored frozen in the site Pharmacy until the first 7 days' supply is to be given to the patient and then every 7 days thereafter. The product once unfrozen should be kept at 2 - 8 °C for a maximum of 7 days.

All patients entering the trial will have been on maximal topical therapy (meaning the maximal labelled dose or frequency of dosing) for at least three months before entry on the study and will continue on this therapy (background therapy) for the duration of the study.

Background therapy:

Patients should continue on whatever topical therapy they are on at the time of screening but this should remain stable during the trial. Lubricants and artificial tears may be used *ad libitum* but should not be administered for 15 minutes before or after the trial medication. In the event of worsening of signs or symptoms that, in the clinician's opinion is so severe as to necessitate a change of medication, ciclosporin and/or antihistamines may be introduced or increased in dose/frequency and this will be considered as a treatment failure for purposes of efficacy analysis. Topical corticosteroids may be added following introduction or increase in ciclosporin/antihistamine therapy if considered necessary.

See Concomitant Medications for further details of choice of eye lubricants.

Patients should not have used topical ocular steroids for 7 days prior to entry to the trial but, at the discretion of the investigator, may receive them as rescue medication during the trial. A comparison of the number of patients requiring rescue therapy at any stage of the trial and the number on such therapy at the end of the trial will be an additional exploratory endpoint.

Use of systemic immunosuppressives, antihistamines or corticosteroids during the trial is forbidden. Patients who, in the opinion of the investigator, require such treatment will be withdrawn from the trial. If the reason for giving such treatment is related to their primary pathology (AKC, VKC, or severe allergic conjunctivitis (SAC or PAC)) they will be regarded as treatment failures.

6.4 Method of Assigning Subjects to Treatments and Blinding (Part 2)

After the initial 3 open label patients (Part 1), subsequent patients entering this clinical trial will be randomised in a 1:1 fashion.

The randomisation will be generated using the 'Prisym Medica Clintrial' software package. The required number of records, along with treatment allocation codes, treatment descriptions and required randomisation block size will be entered into the system according to the study requirements. One master set of codes will be generated within the Prisym system to facilitate printing of labels.

Upon confirmation of a subject's eligibility at the Screening visit, the investigator, or other site personnel under the direction of the investigator, should access the eCRF to register the subject and obtain the Subject Identification number. In addition, the investigator, or designee, will contact the CRO, Tailored Clinical Research Solution (TCRS), to register the subject as randomised. TCRS will forward the Randomisation ID to sites for recording in the patient notes and transcribed eCRF.

6.4.1 Emergency Unmasking for Safety Reasons

In the unlikely event of an emergency where, in the opinion of the investigator, discontinuation of study treatment for an individual patient is not sufficient and the study treatment must be unmasked in order to evaluate further course of action, the investigator will have direct access to the randomisation codes for unmasking.

The investigator will consult his own copy of the randomisation codes supplied in a sealed envelopes individually numbered for each patient and decide what, if any, further action to take.

Once the study treatment has been unmasked, the subject will complete the Early Termination visit and then discontinue study treatment. The subject will also be seen for post-treatment follow-up.

6.5 Compliance

As a measure of compliance, all empty rVA576 vials will be returned by the patient to the site and Patient Dosing Diaries will be reviewed by research staff at each study visit.

6.6 Missed Doses

If a patient misses a dose, it may be taken later unless it is within 3 hours of the next scheduled dose, in which case it should not be taken and the patient should resume normal dosing at the time of the scheduled dose. Precautions about not using other eye drops within 15 minutes before or after the rVA576 dose should continue to be observed.

6.7 Trial Procedures

The total number of clinic visits including screening and follow-up will be a minimum of 7 with additional visits at the discretion of the PI.

The following investigations and diagnostic procedures will be carried out at clinic visits in accordance with the Schedule of Events (i.e. not all evaluations will be carried out at every visit).

By the Investigator

- Medical History, general and indication specific
- Adverse Events
- Post instillation comfort as graded on patient diary cards (five-point grading from 0 (perfectly comfortable) to 4 (Severe, intolerable itching or burning). For full description see Section 6.9.1.

- Clinical examination, gross and slit lamp with clinical scoring. For full description see Section 17.1 (AKC and VKC) and 17.2 (severe allergic conjunctivitis - SAC or PAC).MMP-9 estimation using the *Inflammadry*[®] device
- Conjunctival impression cytology (CIP) (Optional)
- Tear film break up time (TBUT)

By the nurse or other qualified person (these may be done on any order and either before or after the Investigator's examination)

- rVA576 blood levels
- Visual acuity by ETDRS
- Systemic complement activity by serum CH50 ELISA activity.
- Anti-drug antibodies (ADA)
- Pregnancy Test (Urine)

Screening Period:

Potential trial patients will visit the clinic for an initial visit at which time their suitability for the trial will be assessed by the Principal Investigator (PI) and the purpose, nature and possible benefits and risks will be explained. Patients will be given a detailed patient information leaflet and will be given sufficient time to consider their participation before entering the trial.

Patients may enter the trial within 7 days (± 2 days) of screening providing that there has been no change in the inclusion/exclusion criteria. It must be noted when organizing the first dosing visit that the IMP will take 4 days from the Randomisation to be sent to site and to be ready for dispensing.

Part 1- open label: The first 3 patients selected for the study will be treated with active drug in open-label manner at weekly intervals. The first dose to these three patients will be given in the clinic observed by the PI.

Part 2- Randomisation: Upon confirmation of a subject's eligibility at the Randomisation visit, the investigator, or designee, will contact the CRO, TCRS, to register the subject as randomised and obtain the assigned medication number. This information will be recorded in the patient notes and transcribed eCRF.

Dosing Period:

Patients or their carers will collect clinical trial supplies from the clinical trial site at each clinic visit. Between visits new supplies will be delivered from the Pharmacy to the patient's home by a courier service arranged by the Sponsor at a pre-arranged time and date.

Part 1: Patients will be seen by the PI on Day 7 and thereafter every 14 days (± 2 days) during the trial or more frequently if necessary. The trial dosing period will terminate after 56 days' treatment at which time patients will return to the clinic for a final assessment.

Part 2: The remaining 16 patients will be randomised 1:1 to active or placebo and will receive the appropriate medication throughout the trial identified by their Randomisation number.

All randomised patients will be seen and assessed at Day 14 and thereafter at 2 weekly intervals by a masked observer.

Part 1 and Part 2:

Protocol AK701 - version 8.0 10 February 2020 Patients or their carers will be taught how to administer the eye drops. They will also be taught how to store the drug during the trial.

Patients (or their carers) will remove one vial from the refrigerator 10 minutes before administration to allow the vial to warm to room temperature. One drop will be administered topically to each eye using the same vial and same pipette for both eyes.

The drops will be administered twice a day, as near to 12 hours apart as possible (e.g. 8am and 8pm). Vials will be used only once for administration to both eyes. Used vials will be returned to the trial pharmacy at each clinic visit for compliance checking. A daily diary card will be kept in which administration will be recorded together with a record of comfort and any adverse events.

Patients and their carers will be provided with clear written and illustrated instructions detailing the correct procedure for transporting, storing and administering the IMP.

An attempt will be made to collect tear fluid from patients in the trial using either glass capillary tubes or micropipettes according to the method of Sack et al (Sack et al. 1992). However, this may be difficult or impossible in the clinical trial setting as the induction of reflex tearing would obviate the results of the investigation by dilution of the mediators. If sufficient fluid is collected from individual patients (> 10μ L) it will be analysed for complement products and/or LTB4. If insufficient is collected from individual patients any fluid collected may be pooled and analyses done on the total aliquot.

Follow up:

Patient will return again 28 days ± 7 days for a follow-up visit.

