Tear film break up time (TBUT). Tear breakup time (TBUT) is a clinical test used to assess for evaporative dry eye disease. To measure TBUT, fluorescein is instilled into the patient's tear film and the patient is asked not to blink while the tear film is observed under a broad beam of cobalt blue illumination. The TBUT is recorded as the number of seconds that elapse between the last blink and the appearance of the first dry spot in the tear film. A TBUT under 10 seconds is considered abnormal.

This test will be performed in one eye only at the time points specified in the Schedule of Events.

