17.1 Scoring of Clinical Signs and Symptoms – AKC and VKC

| SYMPTOM | 0 | 1 | 2 | 3 |
|--|-------------------------------------|---|--|---|
| ltch | No desire to rub or scratch the eye | Occasional desire to rub or scratch the eye | Frequent need to rub or scratch the eye | Constant need to rub or scratch the eye |
| Tearing | Normal tear production | Positive sensation of fullness of the conjunctival sac without tears spilling over the lid margin | Intermittent, infrequent spilling of tears over the lid margin | Constant, or nearly constant, spilling of tears over the lid margins |
| Discomfort (including burning, stinging, and foreign body sensations) | Absent | Mild | Moderate | Severe |
| Discharge | No abnormal discharge | Small amount of mucoid discharge noted in the lower cul-de-sac | Moderate amount of mucoid discharge noted in the lower cul-de- sac and in the marginal tear strip; presence of crust upon awakening | Eyelids tightly matted together upon awakening, requiring warm soaks to pry lids apart; warm soaks necessary to clean eyelids during the day |
| Photophobia | No difficulty experienced | Mild difficulty with light causing squinting | Moderate difficulty, necessitating dark glasses | Extreme photophobia, causing the patient to stay indoors; cannot stand natural light even with dark glasses |
| SIGN | 0 | 1 | 2 | 3 |
| Bulbar conjunctival hyperaemia | Absent | Mild | Moderate | Severe |
| Tarsal conjunctival papillary hypertrophy | No evidence of papillary formation | Mild papillary hyperaemia | Moderate papillary hypertrophy with oedema of the palpebral conjunctiva and hazy view of the deep tarsal vessels | Severe papillary hypertrophy obscuring the visualization of the deep tarsal vessels |
| Punctate keratitis (superficial epithelial keratitis and punctate staining of the cornea with fluorescein) | No evidence of punctate keratitis | One quadrant of punctate keratitis | Two quadrants of punctate keratitis | Three or more quadrants of punctate keratitis |
| Neovascularization of cornea (new vessel formation, crossing the limbus onto the clear cornea by 2 mm) | No evidence of new vessel Formation | Presence of neovascularization in 1 quadrant of cornea | Presence of neovascularization in 2 quadrants of cornea | Presence of neovascularization in 3 quadrants of cornea |
| SIGN | 0 | 1 | 2 | 3 |

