6.10.2.4 MMP-9 positive levels

The number and percentage of patients with MMP-9 negative (< 40ng/mL) and positive (≥ 40 ng/mL) assessed using the Inflamma Dry device will be presented for each treatment group at each visit for right and left eyes.

All MMP-9 data will be listed.

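### No fixed test order across visits: acuity may be tested before or after the eye examination, and later tests may follow the clinic dose, so some changes from Day 1 may not be like for like

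*Protocol*

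**What the plan says.** Protocol section 6.7 opens its list of tests with "The following investigations and diagnostic procedures will be carried out at clinic visits in accordance with the Schedule of Events". It then gives two lists.

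- **Investigator:** after history, adverse events and diary review come clinical examination with scoring, MMP-9, optional impression cytology and TBUT. No order is stated.
- **Nurse or other qualified person:** this list includes "Visual acuity by ETDRS", and for these tests "these may be done on any order and either before or after the Investigator's examination".

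Fluorescein enters in two places. The AKC/VKC sign table in section 17.1 scores punctate keratitis, described as "superficial epithelial keratitis and punctate staining of the cornea with fluorescein". For TBUT (section 6.9), "fluorescein is instilled into the patient's tear film". The SAC/PAC table in section 17.2 has no corneal or fluorescein item.

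The schedule in section 17.3 heads Day 1 as pre-dose. It also shows drug administration at Days 14, 28, 42 and 56, with no pre-dose label on those visits. PK samples are taken before dosing and one hour after.

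The SAP models acuity (6.10.2.2.2) and TBUT (6.10.2.5.2) as change from Day 1 at Days 14, 28, 42 and 56. It tabulates MMP-9 by visit against a 40 ng/mL cut-off (6.10.2.4).

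**The concern.** A change from baseline is interpretable only if baseline and follow-up are measured under the same conditions. Here acuity may be tested on an untouched eye at one visit and, at another, on an eye that has just had slit-lamp light and dye. TBUT may follow cytology on Day 1 but not at the middle visits. Any ocular test after Day 1 may be done after a study drop given in clinic, whereas Day 1 may not.

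The protocol accepts in one setting that handling the eye can alter a tear measurement. On tear-fluid collection it warns that "the induction of reflex tearing would obviate the results of the investigation by dilution of the mediators". It sets no comparable safeguard for the scheduled ocular tests.

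Acuity, TBUT and MMP-9 are three of the five secondary endpoints. With at most 16 randomised patients, measurement noise that a site instruction could remove is worth removing. An order effect on acuity could also look like a change in vision within an arm.

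**Working it through.** The documents give no figure on test order, so there is none to reproduce. The check compares the section 6.7 lists with the section 17.3 grid, then adds arithmetic for scale.

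**Step 1. Visits set side by side (analysed visits only)**

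| Test | Grid days | What can differ from Day 1 | Later visits unmatched |
|---|---|---|---|
| ETDRS | 1, 14, 28, 42, 56 | before or after the examination (expressly allowed); before or after the clinic dose | any of 4 |
| TBUT | 1, 14, 28, 42, 56 | cytology beforehand on Day 1, if the listed order is followed; clinic dose | 14, 28, 42 (3 of 4) through cytology |
| MMP-9 | 1, 28, 56 | same listed place each time; clinic dose | 0 of 2 through listed order |
| Cytology (optional) | 1, 56 | – | – |

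**Step 2. Clinic dose.** At Days 14 and 56 the one-hour post-dose PK sample leaves a waiting period after the drop. Nothing keeps acuity, scoring or TBUT (or MMP-9 on Day 56) out of it.

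**Step 3. TBUT shift in symbols.** Suppose cytology shortens a following TBUT by c seconds (unknown), and proportions qA and qP of the active and placebo arms have cytology before TBUT on Day 1.

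- Raw mean change at Days 14, 28 and 42 is shifted by qA × c (active) and qP × c (placebo).
- The raw between-arm difference is shifted by (qA − qP) × c, which is zero when uptake is equal.
- Illustration with assumed uptake of 6/8 and 2/8: (0.75 − 0.25) × c = 0.5c.
- The SAP adjusts for baseline TBUT. The middle-visit values are not themselves shifted, so the adjusted difference moves by about b × (qA − qP) × c, where b is the slope of follow-up on baseline. For b between 0 and 1 the illustration gives 0 to 0.5c.
- At Day 56 the raw change is unshifted if cytology preceded TBUT at both visits.

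**Step 4. Noise, for scale only.** Inputs are 8 per arm (16 randomised 1:1) and two-sided 5%. The plan gives no SD or target effect, so units are SDs of the change. By the normal approximation:

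- Detectable difference at 80% power = (1.960 + 0.842) × √(2/8) = 2.802 × 0.5 = 1.40 SD.
- If order adds independent noise of f SD, the same in both arms, the SD is multiplied by √(1 + f²). Power at 1.40 SD is Φ(1.40 / (√(1 + f²) × 0.5) − 1.960).

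| Assumed f | √(1 + f²) | Detectable difference (SD) | Power at 1.40 SD |
|---|---|---|---|
| 0 | 1.000 | 1.40 | 80% |
| 0.25 | 1.031 | 1.44 | 78% |
| 0.5 | 1.118 | 1.57 | 71% |
| 1.0 | 1.414 | 1.98 | 51% |

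**The case against.** The strongest reply is that the plan permits variation but does not show that any occurs, and that several stronger readings fail.

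- **A reader might infer that section 6.7 mandates a harmful sequence for the investigator.** It does not. The lead-in points to the schedule and imposes no order, and the grid lists cytology before MMP-9, the reverse of section 6.7. Wording in the amendment history that required an order is superseded. The gap is an unspecified order.
- **A reader might infer that the tests are shown to disturb one another.** The documents do not say so. The reflex-tearing remark concerns capillary or micropipette collection for complement and LTB4, not MMP-9 or the slit lamp. Any dilution factor, or shortening of TBUT in seconds, would be an assumption.
- **A reader might infer biased MMP-9 changes from Day 1.** The SAP analyses no such change, and the listed place of MMP-9 is the same at each of its visits. At most its level is affected, possibly more in AKC/VKC, where scoring uses fluorescein.
- **A reader might infer a biased treatment effect.** Part 2 is randomised and masked, so order effects are mainly non-differential. The only TBUT p-value is at Day 56, when cytology is scheduled again.

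All of that stands, and it limits the point. It does not answer the express permission for acuity, the missing pre-dose rule after Day 1, or the unmatched TBUT estimates at Days 14, 28 and 42, which the SAP reports with confidence intervals. Nor is the Day 56 match assured: cytology is optional, and section 6.9 does not name the eye used for TBUT. With about 8 per arm and no stratification, cytology uptake could differ between arms by chance.

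**Conclusion.** The point holds in a limited form and should be corrected. Acuity changes from Day 1 can be measured under different conditions at all four later visits. TBUT changes at three of four can be unmatched in patients who have cytology before TBUT on Day 1. Assessments from Day 14 on are not kept ahead of the clinic dose. For MMP-9 the issue is confined to its level relative to 40 ng/mL.

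The expected consequence is avoidable noise in a small comparison and distorted within-arm changes. Its size cannot be derived from the documents; the power figures rest on assumed noise and only show the scale. Bias in the treatment difference would need order or cytology uptake to differ by arm. The primary endpoint, ocular treatment-emergent adverse events, is not shown to be affected.

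**What to change.** In Protocol section 6.7, delete the free-order permission for ETDRS and state one order for every visit, with all ocular assessments before any study drop given in clinic:

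1. ETDRS first, before any drop or contact with the eye.
2. MMP-9, where scheduled, before fluorescein and before any optional tear-fluid collection, which could itself provoke reflex tearing.
3. TBUT and stained scoring in the same order at each visit. Set a fixed interval before TBUT whether or not MMP-9 was sampled; otherwise sampling at Days 1, 28 and 56 but not 14 and 42 would recreate an unmatched TBUT baseline.
4. Impression cytology last.

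Keep free order for the pregnancy test and for bloods with no dose-related time. Also reconcile the MMP-9 row of the section 17.3 grid (Days 1, 28 and 56) with footnote 3, which has the test at all scheduled visits.

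The cost is one paragraph and a site reminder, with slightly less scheduling freedom for site staff. No test, visit or staff member is added.
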